### ***Provider / VA Staff Involvement and Characteristics***

We will recruit approximately 15 VA staff members per site. Staff members from each site will comprise primary care providers, care managers, MH providers, social workers, and administrators (e.g., Primary Care Chief, MH Chief). Given the diversity of VA staff, this sample will include women, men, and members of minority and ethnic groups. This array of providers and staff will allow varied perspective on the CCWV care delivery process at each site.

### **Potential Risks**

Risks are minimal.

For patients, study assessments will include potentially sensitive questions and information about mental and/or physical health symptoms, thus there is risk for embarrassment and negative effects on

patient subjects if sensitive information was improperly disclosed and used in a discriminatory fashion against the individual. It is also possible that patients may become upset or triggered when asked about mental health concerns and exposures, or that suicidal thoughts may be revealed during questionnaire completion or during interviews. Additionally, individuals' social security numbers will be collected in order to obtain data from VA databases and to collect data from patient medical records. If disclosed, this information could cause negative financial or legal consequences. Recruitment may also involve the risk of coercion if the Veteran perceives that refusal might threaten care or benefits.

For staff participants, because these studies ask questions about organizational issues at the clinic where they are employed, there is risk for embarrassment and negative effects on subjects if sensitive information was improperly disclosed and used in a discriminatory fashion against the individual.

However, given the safeguards against improper disclosure and steps we are taking to ensure protection of sensitive information as detailed below, the likelihood of any disclosure is minimal.

### **Adequacy of Protection from Risk**

*Procedures to safeguard against adverse events.* All data collection protocols will include procedures whereby research staff members report problems with the data collection, concerns about risk to subjects or others, or unusual occurrences during the collection. These allow project leaders an opportunity to quickly review and respond to any possible concerns or adverse effects.

*Informed consent.* Research participants are advised of the voluntary nature of participation and research subjects are informed of their right to withdraw from the project at any time. Each participant receives a verbal and written description of the study. The Principal Investigator and delegated research team members are available at all points of the study to answer questions and to explain assessment procedures, uses to which the data will be put, and confidentiality of data.

*Mandatory reporting safeguards.* Procedures to prevent violation of confidentiality are limited by the mandatory nature of legal reporting requirements. Subjects are informed in the consent document and verbal consent process that their responses to the surveys and interviews are confidential, except:

- “1) If we need to protect you or others from harm. An example of this is if you want to hurt yourself or others. In that case, we will give information about you to others that is needed to protect you or others from harm.
- 2) If you tell us about the abuse of a child or of an elderly person, or if you tell us about being abused yourself. In that case, we must report this to a supervisor, who may report it to the authorities.”

*Data safeguards.* Before analysis of the data, all identifying information will be removed from the data. No information that could identify study subjects will be published or presented. Data will be reported only in the aggregate. Identifiable data will be stored separately from coded data sets. Access to identifiable study data will be restricted to research teams on a need-to-know basis.

The CALM CBT program that will be used by care managers who work with patients choosing this option will be accessed from a secure website behind the VA firewall. No mental health information recorded in the program during CALM CBT sessions, including mental health assessments, will be accessed for research purposes. We will document which modules were used for each participating patient as a way of tracking the most useful and effective content for this population.

*Discomfort with assessment, intervention procedures or disclosure safeguards.* During the course of participation in the study, a subject could feel uncomfortable answering the survey or interview questions. All interviewers will be trained in the assessments and with sensitivity to the issues to be discussed. All subjects are informed that they may choose to skip any questions that they find uncomfortable or withdraw from the study at any time.

For patients who consent to be surveyed, the 30-45 minute surveys are handed to the participant by the RA, and will be completed in a private room in the VA clinic setting at each site. The RA will check for completeness as well as suicidality items before participant leaves. Qualitative interviews will be conducted in person in a private room or by phone.

Staff interviews will be conducted over the phone or in person in a private room.

Response procedures for adverse events are described in Section 6 Reporting (below).

*Staff training safeguards.* As required, all research staff will be credentialed by their VA Healthcare System's research service, and will successfully complete all required trainings. Clinical staff provide routine clinical care. Research staff will meet with their local study supervisor (the Site Lead or the Project Director) on a regular basis for supervision, ongoing monitoring of interactions with subjects, and problem solving. Research and clinical staff are trained to identify events that would fall under mandatory reporting guidelines, such as harm to self or others. The PI will be available at all times by cell phone. When the PI is not available, the PI will delegate this responsibility to another qualified, credentialed staff member.

### **Potential Benefits of the Research to Subjects and Others**

Although individual subjects do not benefit directly, there are potential benefits to human subjects from participation. Participants may be able to impact the development and future dissemination of the care models for women with anxiety and/or depression at their own or other VA sites. They may also be able to provide feedback on care in the clinic where they receive services or are employed, which may affect their treatment or working environment in the future if this model is widely adopted.

## **5.2 Recruitment Methods**

This study involves both Veteran **Patients** (n=260; 65/site) and VA **Staff** participants (n=60; ~15/site).

**Patients.** Patient subjects will be recruited after making contact with the CCWV care manager via referral from their provider or other staff. The care manager will introduce the research study, and if the person wishes to find out more about the study and possibly participate, the care manager will introduce the Veteran to the RA (if available), ask the Veteran to complete the Research Candidate contact form, add research staff as an additional signer on their CPRS note to automatically notify research staff of interested individuals, or contact the RA through another secure HIPAA-compliant route such as phone call or encrypted email to relay the Veteran's referral information. . The RA will check in with the care manager frequently to learn when women Veterans have been referred, as well as respond to notifications from the CPRS system, phone calls, and encrypted emails. Using a visit-based sampling method, patients are eligible during their first or second visit with the care manager during the 15-month implementation period. The patient will be informed about the details of research participation and asked if they would like to participate in the project. If they agree, the written or verbal (if by phone) informed consent process will be conducted. Patients that are past the enrollment window (i.e., 1st or 2nd visit with care manager), or otherwise unable or unwilling to participate in surveys are still eligible to complete qualitative interviews.

For patients who enroll after the baseline window and will only be invited to consent to participate in other components of the research (i.e., qualitative interviews, data obtained from medical record) by phone, after receiving information about interested Veterans from the care manager, the RA will mail the interested Veteran a written information sheet about the study that contains all the elements for informed consent and HIPAA, including information about audio recording.. The RA will wait one week before calling the Veteran to check if they have received it. If they have received it, the RA will discuss the details of research participation with the Veteran and if the Veteran would like to participate, the RA will review the written information sheet and conduct a verbal consent process that includes reviewing all the elements of consent and the HIPAA, and verbal consent will be recorded at the time of interview for these patients.

**Staff.** A total of 60 to 80 VA Staff participants will be recruited from 4 sites. Staff participants will be recruited from women's health clinics that are using a WH PACT model of care. To obtain the staff sample, we will work with each site's PBRN Site Lead and/or Site Representative to develop a list of eligible individuals (and their contact information), who meet the staff categories we would like to include. The study PI and/or the Site Lead will present the study to local staff and administrators via email and/or phone call. Staff members will be emailed an invitation to participate in an initial interview, which will be collected at the time of the initial interview. This email will also inform the participant that their participation includes three semi-structured interviews, either in person or over the phone, that will take 30 minutes each, the initial interview in the next few weeks, the second interview 10-12 months later and the final interview about a year later (the expected duration of their participation will be a total of 3 years). The recruitment process will include informing potential staff participants about the study, who is conducting it, why the individual was selected for recruitment, and how the information gathered will be used. Potential staff participants will be informed that their participation is entirely voluntary and their decision about participation will not affect their employment, merit, or promotion. After explaining

the study, if the staff member is interested, the GLA research staff will schedule an appointment, or local staff may help schedule in-person interviews with visiting GLA research staff. We will also inform the participant that in 10-12 months, unless they ask us not to, we will contact them again regarding participating in a similar follow-up interview to document events across time.

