### EMPOWER QUERI Methods

Setting: Women's Health Practice-Based Research Network (PBRN). The PBRN provides a research infrastructure for investigators seeking to increase inclusion of women in VHA research or conduct multi-site women's focused research in VHA. Comprised of 37 VAMCs that see one-third of women Veteran VHA users, the PBRN helps investigators overcome the challenges of multi-site studies through engagement of Site Leads with established working relationships with local clinicians and facility leadership. Site Leads have received implementation training, and have developed across-site relationships through regular national calls and technical support organized by the PBRN Coordinating Center in Palo Alto ([name] LoS).

Modified Stepped Wedge Study Design for Implementation Trials. We will use stepped wedge designs, which rely on sequential roll-out to participating sites over time, while using other sites as controls until they begin implementation. Consistent with our substantial prior experience using these designs in VHA and armed with complexity theory's recognition of nonlinearity of implementation, we will use *modified* stepped wedges (rather than randomized) given their suitability for studying implementation. This design acknowledges that sites are heterogeneous, face multiple constraints, and, as a result, are ready to adopt interventions at different rates. The modified design explicitly considers the timing of implementation spread and addresses the statistical issues introduced by lack of randomization in implementation starts and processes. We will analytically compensate for the design by collecting patient-, provider-, and site-level data that may be associated with timing of the adoption of each intervention.

We will include three levels in our hierarchical stepped wedge models: (1) patient,(2) time of intervention (i.e., when a provider starts using the intervention), and (3) site. Outcomes of interest are measured for all patients at each site within the given intervention time period. We will include four PBRN sites in each of our two implementation trials

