Data collection will occur in each of the REP phases (e.g., pre-conditions for 6 months, pre-implementation for 6 months, implementation for 15 months, and maintenance/evolution for 4 months). Similar to previous modified stepped wedge studies, implementation initiates with PCPs. Figure 4 depicts Site A initiating at Quarter 3, Site B at Quarter 4, and so on, with three PCPs at each site, each quarter, for a total of 81 PCPs. The PCPs "turn on" (i.e., use the template in the CV project; refer to the care manager in the CCWV project) as they switch from pre-implementation to implementation.

Modified stepped wedge designs make efficient use of all data available for within-site and between-site comparisons. For the within-site comparison, sites act as their own controls in an evaluation that compares sites pre- versus post-implementation. The comparison examines sites as they cross-over from control to intervention states. The between-site comparison evaluates the intervention period for a site vs. all other intervention and control periods for all sites. By having these two types of

comparison, the design improves on the validity of the evaluation of the intervention, by accounting for historical time trends that may occur outside of the intervention and for site contextual characteristics that may affect site performance.

We will use a modified stepped wedge design to evaluate the implementation in four VA Women's PBRN sites ([name] LoS). In the context of the modified stepped wedge design, the intervention is "turned on" when a PCP at a site makes her/his first referral to the CCWV care manager (see below).

In Year 1, we will begin the REP pre-conditions phase in one VA Women's PBRN sites. We will continue through the phases over the course of four years, with a 15-month implementation phase in order to ensure adequate time to evaluate implementation and sufficient numbers of Women Veterans being exposed to CCWV. Three additional PBRN sites will be "stepped in" during Year 2 at appropriate intervals over time. According to the REP framework and complexity theory, all sites will be encouraged to adapt and tailor set-up and delivery of CALM according to their local resources and care configurations.

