### REP Implementation Phases

**Pre-conditions (Aim 1):** The need for CCWV has been established and the review of effective interventions has been conducted (see above). To ensure that the care model fits local settings and stakeholder priorities, the PI and Co-Investigator [name] will visit the sites and meet with the local team to discuss local structures, care models and processes, educational needs, as well as elements of the proposed CCWV and tailoring options that we have conceptualized (Table 3). Using the TECH, the local team will discuss options for CCWV implementation and anticipated barriers to implementation. Also during this phase, interviews and surveys will be conducted with all consenting key stakeholders, with the exception of patients who will be interviewed and surveyed in the implementation phase (see below).

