### **Patients**

Inclusion Criteria: female VA patients who are referred to the care manager for further mental health assessment and/or care.

Exclusion criteria: Non-VA patients; less than 18 years of age; anyone who is unable to provide consent.

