### Access, Storage and Handling of Secondary Data

In addition to surveys and interviews, other outcome data will be extracted from national VA data systems, and patient medical record charts. Data from VA electronic data systems will initially include patients' social security numbers (SSN) along with any other identifiers, since these are used to assure that the data matches the project participants. We will merge the extracted data with our existing research data. Once the data have been checked to ensure the merge has been successful, within the shortest possible time period, the SSNs will be removed from the analytic data file and stored in a link file kept in a separate, high security folder on secure VA server. Each subject will already have been assigned a project ID number that does not contain any identifiers. The subject's ID number will replace the SSN in the files. All information linking subject identifiers to their data will be destroyed in accordance with the VA Records Control Schedule and guidance from the CIRB.

VA records data will be obtained from CPRS, DSS or CDW. In order to obtain data, the project team will work with a list of SSNs of patients consented and enrolled in the study. Project or VA-certified database analysts will be given this list of SSNs and will then run a query to extract the needed data, either working in the VINCI platform or downloading the data to a temporary folder on the CSHIIP

secure server. Extracted data will be placed into our secure folder on the local CSHIIP server and coded for analysis. This data will always remain behind the VA firewall.

All the above data are stored and backed up on a secure VA server. Computer users “lock” their workstations when not actively in use and office doors are locked when staff members are not present. Hard copies of sensitive data are stored in a separate locked filing cabinet in a locked office.

Special consideration and precautions will be taken with regard to sharing information provided by individual employees with supervisors and co-workers. While general information derived from employee interviews related to relevant clinical practices, resources, quality improvement activities, and barriers/facilitators will be shared with other site participants in aggregate or synthesized form, detailed information that would allow identification of individual employee responses will not be shared with supervisors of the employees or their co-workers.

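### The stepped-wedge comparison needs patients in the control state, but every patient source described begins after contact with the care manager

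*Combined protocol and SAP*

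**What the plan says.** **What is promised.** Section 5.1 (EMPOWER QUERI Methods) uses sites that have not yet started as controls. Within sites, "sites act as their own controls in an evaluation that compares sites pre- versus post-implementation". Between sites, "The between-site comparison evaluates the intervention period for a site vs. all other intervention and control periods for all sites". On coverage it says "Outcomes of interest are measured for all patients at each site within the given intervention time period". Section 5.6 models the effect of implementation on referral rates. Its power analysis takes a binary patient-level outcome, referred or retained, with the treatment effect at the level of PCP timing. Section 6.0 has the DSMB review adverse events by control and intervention site.

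**What is described.** Under REP Implementation Phases, stakeholders are interviewed and surveyed in pre-conditions "with the exception of patients who will be interviewed and surveyed in the implementation phase". Section 5.4 includes "female VA patients who are referred to the care manager for further mental health assessment and/or care". Section 5.2 states that "patients are eligible during their first or second visit with the care manager during the 15-month implementation period". Women past that window may still join the interviews and records components, but they too come through the care manager. For VA records, the section on secondary data says "the project team will work with a list of SSNs of patients consented and enrolled in the study".

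**The switch.** The intervention turns on "when a PCP at a site makes her/his first referral to the CCWV care manager".

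**The concern.** The design text and the operational text describe two different samples. The first needs women observed while their site or PCP is still in the control state. The second admits only women who have already reached the care manager.

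Three things follow if the plan is carried out as written:

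- The controlled part of Aim 3, meaning the pre/post and between-site contrasts and the PCP-level effect on which power is claimed, has no patient data behind it.
- Reach, named in the Abstract as a primary implementation outcome, has no planned denominator.
- An uncontrolled retention figure, or a rise in referral that the turn-on rule itself creates, could be reported as a stepped-wedge effect and carried into the Implementation Playbook.

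**Working it through.** **1. The plan's own figure.** Section 5.6 states 8.78 referring PCPs per site, rounded to 9, for power 0.80. The inputs are alpha 0.05, at least 260 patients, 4 sites, a plausible retention range of 5% to 85% and effect size variability 0.05. It cannot be reproduced, because no control and intervention rates, no sidedness and no split of control and intervention observations are given. It is neither confirmed nor refuted here.

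**2. Can the exposure effect be estimated?** I used a model with site, quarter and exposure terms. Section 5.1 starts Site A in Quarter 3 and Site B in Quarter 4. I read Sites C and D as Quarters 5 and 6. Fifteen months of implementation is 5 quarters per site.

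| Patients sampled | Site-quarters | Exposed | Control | Rank without exposure | Rank with exposure |
|---|---|---|---|---|---|
| All periods | 34 | 20 | 14 | 13 | 14 |
| Implementation only | 20 | 20 | 0 | 11 | 11 |

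With all periods, the exposure column adds rank and the effect is estimable. With implementation-period patients only it adds nothing. This is a failure of identification, so more patients do not help.

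**3. Outcomes in the enrolled sample.**
- *Referral:* 260/260 = 1, with variance 1 × 0 = 0.
- *Retention among referred women* does vary, but has no control value. Its 95% half-width is 1.96 × √(p(1−p)/260): 2.6 points at p = 5%, 6.1 at 50% and 4.3 at 85%.
- *With PCP clustering:* 9 × 4 = 36 PCPs gives 260/36 = 7.22 women each. The design effect is 1 + 6.22 × ICC. For assumed ICCs of 0.01, 0.05 and 0.10 it is 1.06, 1.31 and 1.62, and the half-width at 50% becomes 6.3, 7.0 and 7.7 points.

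**4. Circular turn-on.** This would remain even with a wider record pull. Suppose records were available for all eligible women of 36 PCPs, 20 or 40 women each, with a constant referral probability of 5%, 10% or 20% and no effect of implementation. These women-per-PCP numbers and rates are assumptions. Turn-on is each PCP's first referral.
- Rate before turn-on: 0% in every setting, by definition.
- Rate after turn-on, leaving out the first referral: about 5%, 10% and 20%.
- A one-sample t-test on within-PCP differences, 1,000 runs per setting, rejected in 91% of runs (20 women, 5%) and in essentially all runs in the other settings. On average 21 to 32 of the 36 PCPs had women on both sides of turn-on and entered the test.

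**The case against.** The strongest reply is that the plan leaves a control-state source undescribed rather than ruling one out. Section 5.1 says that data are collected in each REP phase. The pre-conditions exemption covers patient interviews and surveys, not records. Section 5.5 will obtain utilization history through DART, and that sentence is not expressly limited to enrollees. The sentence on measuring outcomes for all patients ends with the intervention period, so it does not itself promise control data. These points show intent, but none names a source, denominator or extraction for women who were not referred, and the one sentence that defines the records query limits it to consented, enrolled patients. A DART look-back has no stated window and would cover women selected on later referral: a before-after series in exposed women.

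Some PCPs may still be off during a site's implementation phase. Their patients can reach the care manager through other referrers or case finding, but those who enrol have then met the care manager. If turn-on timing is treated as continuous, exposed women are compared with each other.

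Other objections stand in part:

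- The patient total is not consistent. The section on risk to subjects gives 520; section 5.2 gives 260. With 520 the half-width at 50% would be 1.96 × √(0.25/520) = 4.3 points. Section 5.1 gives 81 PCPs, against the 36 used here. Under either patient total every woman is referred.
- The rejection rates in step 4 add little to the logic, since a rate fixed at zero will almost always differ from a positive one. The test is also not the planned three-level model.
- Provider adoption, acceptability and feasibility, the staff interviews and the baseline-to-six-month changes do not depend on control-state patients.

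**Conclusion.** The concern holds, and the plan must be changed. No described patient-level source samples the control state: by the plan's own rules, 0 of 260 women are enrolled at a site before its implementation period. The site-level exposure effect is not estimable from the patients described, whatever their number. The rank result assumes Quarter 5 and 6 starts for the last two sites, but any schedule that samples only exposed site-quarters gives the same answer.

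What the enrolled sample can deliver is retention among referred women, uncontrolled, to within about 6 points at 50%, or 6.3 to 7.7 points under the assumed PCP clustering. The turn-on rule is a second fault that wider data would not remove: it produces a rise from 0% to the ordinary referral rate when nothing has changed. The size of that artefact depends on the assumed rate; its existence does not.

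**What to change.** Reconcile the design, analysis, power and DSMB text with the recruitment, eligibility and records text by one of two routes.

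**(a) Supply the control state.**
- Widen the planned DART/VINCI/CDW extraction to a coded, records-only cohort of all women with a primary care encounter and an anxiety, depression or PTSD indication at the four sites, from the start of pre-conditions through follow-up. The 688 encounters counted at Site 1 show that source records exist.
- Compute reach on that cohort.
- Fit the stepped-wedge model to an outcome observable in both states, for example mental health care engagement or retention within a fixed window after the index encounter.
- Set exposure by the calendar start of implementation at the site or PCP, not by the first referral.
- Keep the consented sample for surveys and interviews.

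Cost: an amended data request, a larger query, an IRB waiver beyond those in section 5.3 (which cover late-enrolling patients and staff), and a rewritten outcome, exposure and power statement. No extra recruitment or visits are needed.

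**(b) Withdraw the claim.** Delete the pre/post, between-site, control-site and powered treatment-effect statements. Report retention as an uncontrolled estimate among referred women with its confidence interval. Cost: text changes only, and a weaker conclusion.
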